10.1.2 Monitoring Adverse Events

All AEs will be assessed by the Investigator and recorded on the eCRF, including but not limited to the following: the event term, the date of onset and resolution, seriousness, severity, relationship to study drug, outcome, treatment of the event, and action taken with the study drug. Adverse events will be reported starting immediately after the subject has provided written informed consent through the EOS Visit (Visit 24/EOS).

Any AE attributed to a protocol-mandated procedure occurring after the subject has provided informed consent but prior to the first dose of study drug should be recorded on the eCRF as an AE.

Adverse events that are not attributed to protocol-mandated procedures occurring after signing of the informed consent but before the first dose of study drug will be reported as medical history.

Example 1:

Thrombophlebitis associated with a blood draw for assessments required prior to dosing per protocol is an event that is related to protocol-mandated procedures. In this scenario, the event of “thrombophlebitis” will be captured as an AE on the eCRF page, and it will be documented as being “unrelated” to study drug as applicable.

Example 2:

An ankle sprain following an unexpected fall from a flight of stairs while at home, after the subject has provided informed consent, but before the first dose of study drug, is clearly unrelated to any protocol-mandated procedures and would therefore be captured as medical history in the medical history section of the eCRF.

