4.0 STUDY DESIGN

This is a multicenter, Phase 3, open-label safety and tolerability study in which approximately 600 subjects will receive open-label NKTR-181 for up to 12 months (52 weeks) from approximately 100 sites. Subjects may include newly enrolled subjects (approximately 250 De Novo Subjects) and subjects who have recently completed Study 14-181-07 or Study 14-181-12 (Rollover Subjects).

The study comprises 3 periods:

- **Screening:** Up to 21 days; Visits 1-2
- **Treatment:** 52 weeks; Visits 3-22
- **Safety Follow-Up:** Approximately 14 days after the last dose of study drug; Visits 23-24

This study will also investigate the PK of NKTR-181 in patients with chronic low back pain or chronic noncancer pain. Blood samples for PK analyses will be collected from all subjects according the Schedule of Assessments (Section 1.2 of protocol), and during a complete 12-hour dosing interval in a substudy of approximately 100 subjects at selected sites.

The three study periods are described in further detail in Study Protocol 14-181-08, Sections 6.1 to 6.3. A schematic of the study design is presented in Section 1.1, and the Schedule of Assessments is presented in Section 1.2 of the protocol.

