8.7.1 Adverse events

A treatment-emergent adverse event (TEAE) is defined as an event that first occurred or worsened in severity after the first administration of study drug (Visit 3) but on or prior to the end of study. Adverse events will be mapped to system organ class (SOC) and preferred term using MedDRA, version 17.1 or later.

The number and percent of subjects who had TEAEs, serious TEAEs, AEs with death outcome, AEs that led to study drug withdrawal, and AE of interest will be summarized. AE of interest is AEs which may indicate potential abuse. The list of abuse related AE of interest is in [Appendix 2](#) to [Appendix 4](#). For withdrawal symptoms (Error! Reference source not found.), only the preferred terms occurred after last dose of treatment will be considered as withdrawal. Adverse events will also be summarized by SOC and preferred term and presented by maximum reported intensity and by Investigator's causality assessment. Corresponding data listings will be presented as well.

An AE that was present at treatment initiation, but resolved and then reappeared while the subject was on treatment, is a TEAE (regardless of the intensity of the AE when the treatment was initiated). If the start date of an AE is incomplete and cannot be categorized as occurring before or after the first dose, then the AE will be considered as TEAE. If the start time of AE is provided then the AE start date and time will be used to classify the AE as TEAE or not. If the

start time is not provided and the AE occurs on the same day of first study drug administration then the AE will be classified as TEAE.

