8.7.2 Clinical and Subjective Opiate Withdrawal Scales

The COWS consists of 11 items to provide a description of the symptoms of withdrawal that can be directly observed by a physician interviewer: increased resting pulse rate, gastrointestinal upset, sweating, tremor, restlessness, yawning, pupil size, anxiety or irritability, arthralgias, piloerection of skin, and runny nose or tearing.

The total score of the COWS is the sum of the responses to the 11 items, which can range from 0 to 48, with higher scores indicating greater withdrawal severity. If there are missing items when the total score is calculated, the total score will be set to missing. Total score between 5 and 12 inclusive indicates mild withdrawal; between 13 and 24 inclusive indicates moderate withdrawal; between 25 and 36 inclusive indicates moderately severe withdrawal; and total score greater than 36 indicates severe withdrawal.

The SOWS is a self-rating scale which has been shown to be a reliable and valid measure of the opiate withdrawal syndrome. It contains 16 symptoms whose intensity the subject rates on a 5-point scale of 0 = not at all, 1 = a little, 2 = moderately, 3 = quite a bit, 4 = extremely. The total

score is a sum of item ratings, and ranges from 0 to 64. If there are missing items when the total score is calculated, the total score will be set to missing.

The total score for COWS and SOWS will be calculated at all scheduled assessment time points.

The COWS and SOWS total scores will be summarized descriptively. The total score of COWS will be summarized categorically by dose level.

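### The abuse-potential adverse event lists have no on-drug window, so Agitation starting after the last dose counts as both abuse potential and withdrawal

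*SAP*

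**What the plan says.** SAP 8.7.1 lists what will be tabulated and ends with "AEs that led to study drug withdrawal, and AE of interest will be summarized". The category is defined in one sentence: "AE of interest is AEs which may indicate potential abuse". The next sentence locates its terms: "The list of abuse related AE of interest is in" Appendix 2 to Appendix 4.

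One timing rule follows, for withdrawal symptoms alone: "only the preferred terms occurred after last dose of treatment will be considered as withdrawal". The cross-reference attached to that rule is broken and prints an error message instead of an appendix number.

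The same section defines a TEAE as an event that first occurs or worsens "after the first administration of study drug (Visit 3) but on or prior to the end of study". SAP 4.0 places safety follow-up at "Approximately 14 days after the last dose of study drug; Visits 23-24". SAP 8.7.2 names "anxiety or irritability" among the 11 COWS withdrawal items.

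**The concern.** A psychoactive symptom on drug may point to abuse potential. The same symptom days after the drug is stopped may point to withdrawal. The SAP recognises this for the withdrawal list, which counts only after the last dose, but gives no matching rule for the other two lists. A post-dose symptom can therefore enter the abuse-potential count.

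This matters because Protocol 2.2 presents reduced CNS effects, including measures of abuse liability, as a feature of the compound. Follow-up is also where withdrawal is expected: Protocol 6.3 says that its COWS and SOWS assessments are there to detect it. Adding post-dose events can only raise the abuse-potential count. If the window were chosen after the data are seen, the choice would look selective in either direction.

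**Working it through.** The plan gives no figure on this point. The check compares the lists, traces one event through the rules, and sizes the window.

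**1. The three lists.** Appendix numbers are inferred from the order of the tables after SAP 10.0; 8.7.6 ties the vital-sign and ECG table to Appendix 1. Terms are counted as they stand in the SAP text available to me, and the withdrawal list may be incomplete there.

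| List | Appendix (inferred) | Distinct terms | Onset rule in 8.7.1 | Shared with withdrawal list |
|---|---|---|---|---|
| Abuse-related | 2 | 11 | none | none |
| Psychotomimetic | 3 | 49 | none | Agitation |
| Withdrawal | 4 | 22 | after last dose | n/a |

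The withdrawal list has 26 entries. Four terms (Agitation, Dyssomnia, Insomnia, Syncope) appear under two system organ classes, so 26 − 4 = 22 distinct terms.

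**2. One Agitation event, by onset and by reading of AE of interest.**

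| Onset | Read as all AEs | Read as TEAEs |
|---|---|---|
| First dose through last dose | abuse potential | abuse potential |
| After last dose to end of study | abuse potential and withdrawal | abuse potential and withdrawal |
| Before first dose | abuse potential, if recorded as an AE at all | not counted, apart from date and time defaults |

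The middle row is the same under both readings, so the post-dose double count does not depend on how the undefined category is read. No precedence rule resolves it.

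Irritability behaves differently. It is on the psychotomimetic list but not on the withdrawal list as I have it. A post-dose report would count as abuse potential only, although COWS treats irritability as part of a withdrawal sign.

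**3. The total.** If Appendix 4 is the withdrawal list, the sentence that places abuse-related terms in Appendices 2 to 4 puts all 22 withdrawal terms inside the abuse-related category. Post-dose nausea, vomiting or insomnia would then enter an abuse-related total. The rule that counts them as withdrawal does not say that they are left out of that total.

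**4. Size of the window.** The off-drug share of the TEAE window is 14 / (T + 14), where T is days on treatment.

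- T = 364 (completer, Visit 22): 14/378 = 3.7%
- T = 180 (assumed): 14/194 = 7.2%
- T = 90 (assumed): 14/104 = 13.5%
- T = 30 (assumed): 14/44 = 31.8%

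These are shares of observation time, not of events. The documents give no rate for Agitation, Irritability or either list.

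**The case against.** The strongest reply is that little is affected. Only one term is shared by name, and none of the 11 abuse-related terms is on the withdrawal list. Irritability is half of one COWS item, not a withdrawal-list term. Events are also tabulated by preferred term and listed (SAP 8.7.1), so post-dose Agitation can be traced. Aberrant drug behaviour is a key safety endpoint through MADDERS, which distinguishes withdrawal from abuse and is adjudicated (SAP 5.0 and 8.7.4). Withdrawal has its own scales. On this view, AE of interest is a supplementary descriptive count in an uncontrolled study. This stands as a limit on size: a reader might call the count uninterpretable, but these other outputs mean that it is not. It does not remove the gap, because the count is planned and its window is undefined.

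A second reply is that one term may properly sit on two labelled lists, and that forcing post-dose Agitation into withdrawal presumes its cause. That is fair, and the fix below avoids it.

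A reader might also infer that symptoms during the pre-treatment opioid taper count as abuse-potential events of NKTR-181. The documents do not establish that. The SAP never says that AE of interest reaches back before the first dose. Protocol 10.1.2 records as AEs only events within "Any AE attributed to a protocol-mandated procedure occurring after the subject has provided informed consent but prior to the first dose of study drug"; other pre-dose events go to medical history. A taper symptom would have to be attributed to a mandated procedure, and the category would have to mean all AEs. Rollover Subjects have no Visit 2 taper. Under the TEAE reading, two narrow routes remain: an event on the first-dose day without a start time, and a missing start day in the first-dose month.

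**Conclusion.** The point holds for the period after the last dose. As written, the abuse-related and psychotomimetic counts include about 14 off-drug days, and Agitation in that period counts as both abuse potential and withdrawal. The range Appendix 2 to Appendix 4 appears to add the withdrawal list to the abuse-related category, subject to the inferred numbering. Any effect is upward, against the drug.

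The size is unknown and may be small. For a completer, 3.7% of the TEAE window is off drug. The share rises with early termination, and the Schedule of Assessments notes that taper drug is not dispensed at early termination. A number of extra subjects would need on-drug and off-drug rates that the documents do not give, so none is offered. It would be too strong to say that withdrawal symptoms in general are counted as abuse potential through the two abuse-potential lists: the overlap shown is Agitation by name and Irritability through COWS. The pre-first-dose route is a question of wording to settle, not a finding.

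**What to change.** In SAP 8.7.1, before analysis:

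- State that AE of interest means TEAE. This also closes the pre-dose question, apart from the two date and time defaults.
- Report abuse-related and psychotomimetic terms in two columns: onset from first dose through last dose, and onset after the last dose. Name the on-drug column as the abuse-potential incidence.
- Report the withdrawal list as its own category, outside the abuse-related total.
- Flag post-dose Agitation as overlapping with withdrawal and do not add it to the on-drug count. No cause needs to be assigned.
- Repair the broken cross-reference and give the appendix number for each list.

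The cost is a few sentences, a date filter and one extra table split, with no new data. The downside is that an event starting soon after the last dose moves to the post-dose column, where it stays visible. The split also cannot separate withdrawal arising during the one-week end-of-treatment taper, which falls before the last dose; a footnote should say so.

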Study Design:	
Open-label, multicenter, safety and tolerability study of NKTR-181 in the treatment of moderate to severe chronic low back pain or chronic noncancer pain.
 
The study will be divided into the following 3 periods:
 
 Screening: Up to 21 days Treatment: Up to 52 weeks (inclusive of a 1-week taper) Follow-up: Approximately 14 days after last dose of study drug

Test Product, Dose and Mode of Administration:	
Name: NKTR-181 tablet(s)
 
Dose, Route, and Frequency: NKTR-181 100-mg and 200-mg tablets will be administered orally twice daily (BID) as doses of 100 mg, 200 mg, 300 mg, 400 mg, 500 mg and 600 mg BID. Each dose will consist of tablets as follows:
 
100-mg dose = 1 x 100-mg tablet
 
200-mg dose = 1 x 200-mg tablet
 
300-mg dose = 1 x 200-mg tablet + 1 x 100-mg tablet
 
400-mg dose = 2 x 200-mg tablets
 
500-mg dose = 2 x 200-mg tablet + 1x 100-mg tablet
 
600-mg dose = 3 x 200 mg tablet
 
Subjects should take NKTR-181 BID at approximately 8 AM and 8 PM.

Safety:	
Key Safety Endpoints:
 
Safety and tolerability will be evaluated based on the following:
 
 • Incidence, type, seriousness, and severity of adverse events (AEs) reported • Clinical laboratory evaluations • Electrocardiograms (ECGs) • Vital signs (respiratory rate, pulse, heart rate, blood pressure, and temperature) • Drug withdrawal as measured by the Clinical Opiate Withdrawal Scale (COWS) and the Subjective Opiate Withdrawal Scale (SOWS) • Incidence of aberrant drug behavior according to MADDERS™ assessment • Suicidality assessment (Columbia-Suicide Severity Rating Scale [C-SSRS])
Efficacy:	
Efficacy Endpoint:
 
 • Efficacy will be evaluated based on the mBPI-SF administered at clinic visits.
Pharmacokinetics:	
Plasma concentrations of NKTR-181 and selected metabolites will be tabulated by time and subject and assessed for relationship to dose during the treatment phase. These data will be pooled with those from other studies during population PK analyses and investigation of exposure-response relationships for efficacy and safety.

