16. De Novo Subject undergoing opioid taper will have COWS administered at Visit 2. All subjects will be administered COWS at Visit 3. COWS score must be ≤ 12 to enter the Treatment Period.
17. De Novo Subjects taking opioid analgesics at Visit 2 will complete a SOWS assessment daily while tapering their opioids over the next 7-14 days. All subjects will complete the SOWS on the two days prior to Visit 21 and daily between Visits 21 and 22. Subjects will then complete the SOWS twice daily for three days following the last dose of study drug (i.e., following Visit 22), then daily for the remainder for the study (i.e., through Visit 24).
18. A PK sample will be collected on all subjects at Visit 3. PK sample at Visit 3 must be collected prior to the subject taking the first dose of study medication for De Novo Subjects.
19. For subjects participating in the PK substudy, the dosing period PK collection may be completed when a stable dose has been identified. This may occur as early as the second visit following the start of a dose level. Subjects will be reminded to *not* take their AM dose on the planned dosing period PK collection visit. A predose sample will be obtained and the subject will take their AM dose in the clinic. PK samples will be obtained 0.5, 1, 2, 3, 4, 5, 6, 8, and 12 hours postdose.
20. Dispense taper study drug only for subjects completing study. Taper study drugs are not dispensed at Early Termination.
21. Study drug is not dispensed at Visit 22/EOT. Final study drug and rescue medication reconciliation conducted at Visit 22/EOT.
22. Collection of concomitant medications and adverse events will start after the signing of the ICF through study completion.

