2.3 Study and Dose Rationale

This study is designed to provide adequate safety data in subjects with chronic low back pain or chronic noncancer pain in order to fulfill ICH requirements for new chemical entities. The dose range to be utilized is 100-mg NKTR-181 twice daily (BID) to 600-mg NKTR-181 BID. This dose range has been established based upon safety, tolerability, pharmacokinetic (PK), and pharmacodynamic (PD) data from three Phase 1 studies and the findings of a completed Phase 2 study in opioid-naïve subjects with moderate to severe chronic pain due to osteoarthritis of the knee. Phase 1 multiple ascending dose (MAD) studies established a dose that was not tolerated in opioid-naïve, healthy subjects (500-mg NKTR-181 every 12 hours [q12h]) and demonstrated 400-mg NKTR-181 q12h to be a safe and well-tolerated dose. In both studies, pupillometry

demonstrated robust CNS mu-opioid agonist effects consistent with known, approved extended-release/long-acting (ER/LA) opioids.

Evidence supporting the minimum dose of 100-mg NKTR-181 BID comes from the Phase 1 clinical program and a completed Phase 2, enriched-enrollment, randomized withdrawal design study in approximately 200 subjects with moderate to severe chronic pain due to osteoarthritis of the knee. In this Phase 2 study, 49% of subjects were randomized at 100-mg NKTR-181 BID and an average 40% reduction in average daily pain scores was demonstrated during the open-label titration period, consistent with known, approved opioid analgesics.

Recently, over 330 opioid-naïve subjects gradually titrated to a dose of 400mg q12h in the ongoing Phase 3 study (14-181-07) have shown a good safety and tolerability profile. In addition, the current long term safety study (14-181-08) and the second efficacy study (14-181-12) both allow inclusion of opioid-experienced subjects who are expected to tolerate higher doses of NKTR-181. Thus, titration to a maximum dose of 600mg q12h will be allowed in a measured step-wise approach starting at the lowest dose available so as to ensure tolerability while managing chronic pain.

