Following 51 weeks of NKTR-181 treatment, subjects will begin a 1-week taper from study drug. The NKTR-181 dose will be decreased over the 1-week period until all subjects are receiving 100-mg BID for at least 2 days. Subjects will return to the site for their End of Treatment visit (Visit 22/EOT). Following completion of Visit 22/EOT **or** completion of an ET Visit at any time after receiving study drug, subjects will proceed to the Safety Follow-Up Period.

The COWS and SOWS will be administered according to the Schedule of Assessments (Section 1.2) to monitor for opioid withdrawal. Subjects experiencing opioid withdrawal will be treated appropriately according to the Investigator's clinical practice.

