Nervous system disorders	Neurological disorders NEC	Paraesthesias and dysaesthesias	Hypoaesthesia
Psychiatric disorders	Disturbances in thinking and perception	Perception disturbances	Illusion
	Personality disorders and disturbances in behaviour	Behaviour and socialisation disturbances	Indifference
	Mood disorders and disturbances NEC	Emotional and mood disturbances NEC	Irritability
	Dementia and amnesic conditions	Amnesic symptoms	Memory impairment
	Cognitive and attention disorders and disturbances	Cognitive and attention disorders and disturbances NEC	Mental impairment
	Mood disorders and disturbances NEC	Fluctuating mood symptoms	Mood swings
Musculoskeletal and connective tissue disorders	Muscle disorders	Muscle tone abnormalities	Muscle rigidity
Psychiatric disorders	Sleep disorders and disturbances	Parasomnias	Nightmare
Nervous system disorders	Neurological disorders NEC	Paraesthesias and dysaesthesias	Paraesthesia
Psychiatric disorders	Personality disorders and disturbances in behaviour	Behaviour and socialisation disturbances	Paranoia

System Organ Class	Higher Level GT	Higher Level Term	Preferred term
	Schizophrenia and other psychotic disorders	Psychotic disorder NEC	Psychotic disorder
Nervous system disorders	Neurological disorders NEC	Sensory abnormalities NEC	Sensory disturbance
Psychiatric disorders	Disturbances in thinking and perception	Delusional symptoms	Somatic delusion
		Perception disturbances	Somatic hallucination
	Psychiatric and behavioural symptoms NEC	Abnormal behaviour NEC	Staring
	Sleep disorders and disturbances	Dyssomnias	Stupor
	Disturbances in thinking and perception	Thinking disturbances	Thinking abnormal
			Thought blocking
Schizophrenia and other psychotic disorders	Brief psychotic disorder	Transient psychosis	

***Drug Withdrawal- Related Adverse Events Occurring Following Drug Discontinuation
 (Preferred Terms; MedDRA 18.0)***

System Organ Class	Preferred term
Cardiac disorders	Syncope
Gastrointestinal disorders	Vomiting
	Diarrhoea
	Nausea
General disorders and administration site conditions	Hyperhidrosis
	Pain
Musculoskeletal and connective tissue disorders	Chills
Nervous system disorders	Headache
	Agitation
	Dyssomnia
	Insomnia
	Poor quality sleep
	Syncope
	Terminal insomnia (lower level term of interest: early morning awakening)
	Tremor
Psychiatric disorders	Agitation
	Anhedonia
	Anxiety
	Dysphoria
	Dyssomnia
	Dysthymic disorder
	Feeling of despair
	Insomnia
	Morose
	Negative thoughts
	Nervousness

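### Withdrawal AEs count only after the last dose, so completers' taper-week events go unlabelled while early terminators' stop from current dose is covered

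*SAP*

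**What the plan says.** SAP 8.7.1 plans a summary of adverse events of interest, with term lists in the appendices. For the withdrawal list it adds a timing condition: "only the preferred terms occurred after last dose of treatment will be considered as withdrawal". The list itself is titled to match, with the words "Related Adverse Events Occurring Following Drug Discontinuation". The SAP does not define the last dose for this rule.

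The protocol fixes where that dose falls for a subject who completes:

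- Section 6.2: "Following 51 weeks of NKTR-181 treatment, subjects will begin a 1-week taper from study drug". It then says: "The NKTR-181 dose will be decreased over the 1-week period until all subjects are receiving 100-mg BID for at least 2 days".
- The synopsis gives the treatment period as up to 52 weeks, "inclusive of a 1-week taper".
- Footnote 17 to the Schedule of Assessments treats the end of dosing as the end of the taper. SOWS goes to twice daily for the "three days following the last dose of study drug (i.e., following Visit 22".

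For subjects who leave early, footnote 20 says: "Taper study drugs are not dispensed at Early Termination".

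Two other rules bear on the taper week. SAP 8.7.1 runs the general TEAE window from first dose to end of study. Protocol 10.10 has SOWS completed daily between Visits 21 and 22 and COWS done at both visits, and SAP 8.7.2 summarises the total scores of both scales.

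**The concern.** The protocol handles the taper as a time when withdrawal may appear. Section 6.2 follows the taper instruction directly with monitoring for opioid withdrawal, and SOWS becomes daily. The SAP's AE rule does not open until that week is over. For completers, the withdrawal label can therefore attach only to events after the final step from 100 mg BID to nothing. For early terminators it can attach to events after an abrupt stop from whatever dose they were taking, which includes non-responders discontinued at 600 mg BID.

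If the summary reports one percentage over all subjects, it combines two different exposures under one name. The completers, who have the longest exposure in a long-term safety study, are the ones whose count can be too low.

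The general TEAE tables do not repair this. The listed terms include nausea, vomiting, headache and insomnia, and in tables covering a year of treatment a reader cannot pick out the events of the taper week.

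**Working it through.** The SAP states no figure on this point, so there is nothing to reproduce. The check has three steps.

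**1. When the window opens.** Visit 21 is at Day 357 and Visit 22 at Day 364, each with a window of +3 days (Schedule of Assessments). The taper lasts 364 − 357 = 7 days. The synopsis counts it inside the 52 weeks (52 × 7 = 364), and footnote 17 places the last dose at Visit 22. The withdrawal window for a completer therefore opens at about Day 364. Reading the last dose as the last pre-taper dose would remove the problem, but it would contradict both of those places.

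**2. How much dose reduction precedes the window.** Doses run from 100 to 600 mg BID in 100-mg steps (Protocol 2.3 and 6.2), and every taper ends at 100 mg BID. For a completer on D mg BID before the taper:

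- share of the reduction made before the last dose = (D − 100)/D
- share made at the last dose = 100/D

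| D (mg BID) | Reduction during taper (mg BID) | Share before window opens | Share after last dose |
|---|---|---|---|
| 100 | 0 | 0% | 100% |
| 200 | 100 | 50% | 50% |
| 300 | 200 | 67% | 33% |
| 400 | 300 | 75% | 25% |
| 500 | 400 | 80% | 20% |
| 600 | 500 | 83% | 17% |

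More than half of the reduction precedes the window at 300 mg BID and above, exactly half at 200, and none at 100. For an early terminator, the whole stop from current dose falls after the last dose and so inside the window.

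**3. Length of observation.** Follow-up runs about 14 days after the last dose. From the start of the taper to the end of follow-up is 7 + 14 = about 21 days for a completer. The rule leaves 7 of those 21 days (33%) without the withdrawal label. An early terminator has about 14 days, all of them eligible.

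**The case against.** The case for leaving the rule alone has real parts.

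- **The endpoint covers the taper.** A reader might infer that the key withdrawal endpoint misses the taper. It does not. Protocol section 1.0 and SAP 5.0 define that endpoint by COWS and SOWS. Both are collected across the taper, and SAP Table 1 keeps Visits 21 and 22 for COWS. This stands. However, the scales give total scores (and COWS categories), not an incidence of withdrawal AEs, so they do not correct the AE summary.
- **The events are not lost.** A reader might infer that taper-week events drop out of safety reporting. They remain TEAEs, tabulated by SOC, preferred term, intensity and causality, and listed. Only the withdrawal label is withheld.
- **The rule is coherent.** It matches the title of the list and favours specificity. Nausea, headache or pain in a subject still taking an opioid may be a drug effect or returning pain. This is a good reason to keep the post-last-dose count as it stands. It is not a reason to leave the taper week unseen.
- **The percentages are not a bias estimate.** A reader might take 83% as the fraction of withdrawal events missed. The documents give no event rate and no distribution of stable doses, so that cannot be derived. Nor does the larger share apply to every completer, since it is 0% at 100 mg BID.
- **No comparison of completers with early terminators is planned.** That is correct, and the two groups differ by design. The difficulty lies in the pooled figure, which needs no planned comparison to be misread.
- **Early terminators are not a pure contrast.** Protocol 6.2 allows stepwise reductions for tolerability, so some will have come down before stopping. The claim is therefore limited to the stop from their current dose.

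**Conclusion.** The point holds as a labelling and comparability problem in one planned safety summary. A completer's listed event with onset in the taper week is never classed as withdrawal, while an early terminator's stop from current dose falls wholly inside the window. A pooled percentage mixes the two and can understate withdrawal AEs in completers.

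In dose terms the part before the window ranges from 0% to 83%, depending on the dose before the taper. The number of events affected is unknown.

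The conclusion assumes that the last dose means the last dose of study drug taken, at the end of the taper, as the protocol's schedule and synopsis imply. The primary objective and the COWS/SOWS endpoint are not affected. The change is worth making before analysis because the count is understated by construction and the repair is cheap.

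**What to change.** In SAP 8.7.1, define the last dose for this rule as the last dose of study drug, taper included. Then:

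1. Keep the post-last-dose count unchanged, in its own column.
2. Add a second column, for subjects who taper, with listed terms whose onset or worsening falls between the first taper dose (Visit 21) and the last dose.
3. Show both columns by completer and early-termination status.
4. State in the table note that observation is about 21 days for subjects who taper and about 14 days for early terminators. Do not merge the columns into one rate, since that would replace one unequal comparison with another.

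The cost is SAP wording and one more column. Protocol 10.1.2 already requires AE onset dates, so no new data are needed and no study procedure changes. The drawback is that some non-specific taper-week events unrelated to withdrawal will appear in the added column. Keeping it separate lets the reader discount them.
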